## 6.2 Potential Benefits

The study participants may receive no benefit. However, possible benefits include an increase in vitamin D status or resolution of vitamin D deficiency/insufficiency. However, subjects may not receive any benefit. The subjects' being in the study may help the investigators evaluate whether the SoliusONE device is safe and effective in increasing blood levels of 25-hydroxyvitamin D and treating vitamin D deficiency/insufficiency. Subjects will not be responsible for any research related costs. They will receive compensation in each of their visit, which is shown below. Parking vouchers or transportation cost are available for each visit.

Study group/activity	Screening visit Wk 1	Titration					Intervention				Total	
		Wk 2	Wk 3	Wk 4	Wk 5	Wk 6	Wk 7	Wk 8	Wk 9	Wk 10		
Activity	Screening Consent BD	BD UV	UV	UV	UV	UV	BD *2 UV	UV	UV	UV BD*2	\$750	Up to \$1,050
Compensation	\$100	\$50	\$50	\$50	\$50	\$50	\$50	\$50	\$50	\$250		
Transportation cost	PV or \$30	PV or \$30	Up to 300									

Note: BD: Blood draw; UV: Ultraviolet B radiation exposure; PV: Parking voucher

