### 6.3 Analysis of Risks in Relation to Benefits

Highly trained professionals will be performing the blood draws which is likely to be a chance of risk. The adverse skin reaction from the Solius Photobiological System such as skin erythema and pruritus is a possible risk in this study. However, this study will expose the participants to a relatively low intensity of UVB (0.6 MED), so the risk of adverse reaction is minimal. All the participants will be asked for their willingness to receive the intervention at every exposure and will be questioned and examined for any potential adverse reaction due to the intervention. If any significant adverse reaction is detected, the intervention will immediately stop and the affected participant will receive immediate medical attention. Significant adverse reactions include photokeratitis, moderate to severe skin tenderness, itchiness and tightening, skin blistering, or bruising or tearing of skin. The risks of breach of confidentiality are highly unlikely, and therefore benefits will greatly outweigh the risks.

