## 10.2 Safety Review

[name] or [name] will interview the subjects before their next exposure each week for any adverse events including erythema or any other skin reactions as shown in the table. At the time of the evaluation, it will be determined whether the subject will continue with the next exposure or whether the subject will be removed from the study. This will be based on the determination of the degree of erythema or adverse skin reaction. [name] will serve as an Independent Scientific Reviewer (ISR). He will provide an assurance that the findings and conclusions reached are supported by the data presented, and also, to assure that the content is consistent with applicable scientific standards and will be responsible for a review of the data analysis, data interpretation and/or presentations and manuscripts.

The following known side effects of UVB will be monitored:

Side effect	Signs/symptoms	Instruction for subjects on monitoring
Sunburn	Pain, tenderness of the skin, redness, tightness, itching, and rarely blistering	Check for pain and redness 4-6 hours after treatment. If there is severe pain, should seek medical attention.  If there are blisters, should seek medical attention
Photoaging	Atrophic skin, coarseness, fibrotic areas, increased fragility, laxity, mottled pigmentation, telangiectasias, wrinkling	If there is increased fragility (i.e. easy bruising or tearing of skin), then should seek medical attention. The other photoaging side effects are benign and more of a cosmetic nature.
Tanning	Skin darkening	As a benign side effect, no subject monitoring is needed

In addition, Prior to each treatment, Solius software will prompt the user with the following questions to assess erythema:

1. *Did you observe any pinkness (similar to sunburn) after your last treatment? (yes / no)*
2. *Did the pinkness last for more than 3 days? (yes / no)*
3. *Did you experience any pain or discomfort (excluding itch) with the pinkness? (none / mild / moderate/severe)*

Based on the user's response, the software could maintain current dose, reduce dose, or block account for further investigation. The PI or [name] or [name] will be notified to perform further assessment if an account was blocked by the software.

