### 10.4 Stopping Rules

A subject will be withdrawn from the study if refuse to participate, or if subject's serum 25(OH)D level is more than 100 ng/mL, or if the subject undergoes an adverse reaction to the light source e.g. skin erythema or pruritus.

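### Per-visit pay weighted to Wk 10, combined with withdrawal for any skin reaction, gives subjects a financial reason not to report mild reactions and puts the safety result at risk of bias

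*Combined protocol and SAP*

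**What the plan says.** **Payment.** Section 6.2 states "They will receive compensation in each of their visit, which is shown below". Its table gives $100 at Wk 1, $50 at each visit from Wk 2 to Wk 9, and $250 at Wk 10. Transport is separate: "Parking vouchers or transportation cost are available for each visit".

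**What follows a reaction.** The sections differ:
- Section 10.4 withdraws a subject "if the subject undergoes an adverse reaction to the light source e.g. skin erythema or pruritus". It sets no severity threshold and makes no exception for titration.
- Section 6.3 uses a threshold: "If any significant adverse reaction is detected, the intervention will immediately stop". It then defines the term: "Significant adverse reactions include photokeratitis, moderate to severe skin tenderness, itchiness and tightening, skin blistering, or bruising or tearing of skin".
- Section 10.2 has staff choose between continuing and removal: "This will be based on the determination of the degree of erythema or adverse skin reaction". It adds a software response: "Based on the user's response, the software could maintain current dose, reduce dose, or block account for further investigation".
- Sections 6.1 and 8 treat a skin reaction in titration as the event that ends escalation and fixes the subject's dose.

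**How reactions are found.** Section 4.1.1 lists adverse events and skin changes as endpoint measure 1, obtained by asking subjects at each visit. Under Section 10.2, staff "will interview the subjects before their next exposure each week for any adverse events", and the software asks about pinkness after the last treatment. Section 6.3 adds an examination at every exposure.

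**Early exit.** Section 9 requires a final blood sample before a subject is removed. It does not say whether that sample is paid for.

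**The concern.** Three features combine. Pay accrues by attendance, one third of it falls on the last visit, and the strictest stopping text ends participation for the mildest kind of reaction. A subject who notices slight redness or itch then has a financial reason to say nothing.

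Self-report carries most of the weight. Section 10.2 tells subjects to check for redness 4 to 6 hours after treatment, but staff see them about a week later, when it may have settled. The software's discomfort question excludes itch, so pruritus depends on the interview and the examination.

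At stake is endpoint measure 1. Any under-reporting would make the device look better tolerated than it is, and Section 3.2 says this study prepares for a larger one on safety and efficacy. In titration there is a further consequence: a reaction that is neither reported nor seen can be followed by the next step, 26 to 36% higher, unless the maximum has been reached.

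**Working it through.** **Inputs.** The compensation table in Section 6.2, the withdrawal rule in Section 10.4, the early-exit sample in Section 9, and 10 treated subjects (Section 8). Transport is left out of the loss because it reimburses a cost.

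**Reproducing the plan's total.** 100 + 8 × 50 + 250 = $750, as stated. Adding 10 × 30 = $300 for transport gives the stated maximum of $1,050. The Wk 10 share is 250/750 = one third.

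**Loss on withdrawal.** The first exposure is at Wk 2, so Wk 3 is the first visit at which a reaction to an earlier exposure can be reported. For a report at week w:
- A: visit w is paid and all later payments are lost. For w = 3 to 9, loss = (9 − w) × 50 + 250.
- B: visit w is also unpaid (for example, the subject telephones before attending). Loss = A + 50 for w = 3 to 9.
- C: as A, but the $250 is paid for the early final sample. Loss = A − 250. This payment is an assumption; the text is silent.

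| Report at | A | B | C |
|---|---|---|---|
| Wk 3 | $550 | $600 | $300 |
| Wk 4 | $500 | $550 | $250 |
| Wk 5 | $450 | $500 | $200 |
| Wk 6 | $400 | $450 | $150 |
| Wk 7 | $350 | $400 | $100 |
| Wk 8 | $300 | $350 | $50 |
| Wk 9 | $250 | $300 | $0 |
| Wk 10 | $0 | $250 | $0 |

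Under A, the loss is 550/750 = 73% of all pay at Wk 3, 350/750 = 47% at Wk 7 and 250/750 = 33% at Wk 9.

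**Which rows depend on which rule.** Wk 3 to Wk 6 are titration weeks. Their losses under A ($550 down to $400) arise only if Section 10.4 overrides the titration rule in Sections 6.1 and 8. If the titration rule governs, the reaction fixes the dose, the subject continues, and the report costs nothing. For reports at Wk 7 to Wk 9, the range under A is $350 down to $250.

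**What under-reporting would do (illustration only; the rates are assumed).** With 10 subjects, one concealed reactor lowers the observed rate by 1/10 = 10 percentage points. Suppose the true reaction rate is 20%. The chance that no reaction is reported is then:
- full reporting: (1 − 0.20)^10 = 11%
- a quarter unreported: (1 − 0.15)^10 = 20%
- half unreported: (1 − 0.10)^10 = 35%

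**The case against.** The strongest reply is that withdrawal is only one of several stated consequences. A reader might infer from Section 10.4 that every report of mild redness or itch ends participation. The documents do not support that: under Sections 6.3 and 10.2 a mild reaction need not stop anything, and under Sections 6.1 and 8 a reaction in titration sets the dose. This stands, and it makes the upper losses conditional. It does not remove the incentive, because a subject cannot know in advance which rule will be applied, and the section headed as stopping rules is the strictest.

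A second reply is that forfeiture of later pay is itself an inference. This also stands. Nothing in the text states it, the consent pages were not available and may settle it, and the required early sample might earn the $250.

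Third, a reader might infer that the safety endpoint is biased. The documents hold no data on under-reporting. They provide a weekly interview, software prompts, an instruction to telephone about side effects, and an examination at each exposure. These are real safeguards. A weekly examination can still miss redness or itch that has settled, so a risk of bias remains, and no more than that is shown.

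Lastly, this is a 10-subject, single-arm feasibility study that tabulates adverse events without a test. That limits the weight of the point. It does not argue against a cheap correction.

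**Conclusion.** The point holds in conditional form. Per-visit pay weighted to Wk 10, together with a literal reading of Section 10.4, gives subjects a financial reason not to report mild reactions. With the reporting visit paid and no protection of later pay, the possible loss runs from $550 at Wk 3 to $250 at Wk 9. It reaches $600 if the Wk 3 visit is unpaid, and falls to $300 at Wk 3 and $100 at Wk 7 if an early final draw earns the $250.

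This rests on two assumptions: that no payment protection exists in the consent text, and that Section 10.4 is the rule applied. The titration-week figures need the second assumption in particular.

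Any resulting bias would be toward fewer reactions. Its size cannot be estimated from the documents. The change is worth making because it is cheap and requires no clinical rule to be chosen.

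**What to change.** In Section 6.2, with matching consent text:
1. State that a subject whose UVB is stopped for a reaction keeps the remaining scheduled payments on giving the remaining blood samples or the early final sample required by Section 9. This must include the UV-only visits (Wk 3 to Wk 6, Wk 8 and Wk 9). If only blood-draw visits were protected, a subject stopped at Wk 3 with that visit paid would still lose 5 × 50 = $250.
2. Attach the $250 to the end-of-study blood draw, not to completing UVB, and say that an early final draw counts.
3. Tell subjects that reporting a reaction does not reduce their pay. This is true only if item 1 is in place.

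Separately, reconcile Sections 6.1, 6.3, 8, 10.2 and 10.4 on what follows a skin reaction. The choice of rule is for the sponsor and the investigator.

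The cost is an edit to the compensation text and the consent form. The per-subject maximum stays at $750 plus transport. The small downside is that some payment is made without a UVB exposure. If the consent form already protects pay, Section 6.2 need only be brought into line with it.

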### 6.3 Analysis of Risks in Relation to Benefits

Highly trained professionals will be performing the blood draws which is likely to be a chance of risk. The adverse skin reaction from the Solius Photobiological System such as skin erythema and pruritus is a possible risk in this study. However, this study will expose the participants to a relatively low intensity of UVB (0.6 MED), so the risk of adverse reaction is minimal. All the participants will be asked for their willingness to receive the intervention at every exposure and will be questioned and examined for any potential adverse reaction due to the intervention. If any significant adverse reaction is detected, the intervention will immediately stop and the affected participant will receive immediate medical attention. Significant adverse reactions include photokeratitis, moderate to severe skin tenderness, itchiness and tightening, skin blistering, or bruising or tearing of skin. The risks of breach of confidentiality are highly unlikely, and therefore benefits will greatly outweigh the risks.

## 7 Study Subject Selection

### 7.1 Subject Inclusion Criteria

In order to be eligible to participate in this study, an individual must meet all of the following criteria:

1. Age at least 22 years old
2. Male or Female
3. Skin Type I-VI
4. Women of child bearing potential must be on birth control and not pregnant based on a negative pregnancy test at baseline.
5. Ability and Willingness to give informed consent and comply to protocol requirements
6. Serum total 25(OH)D < 30 ng/mL

### 7.2 Subject Exclusion Criteria

An individual who meets any of the following criteria will be excluded from participation in this study:

1. Ongoing treatment with supplemental or pharmacological doses of vitamin D, vitamin D metabolites or analogues
2. Pregnant
3. History of underlying photosensitivity
4. Use of medications that cause a photosensitivity reaction (including but not limited to): tetracycline, tretinoin, amiodarone, doxycycline, naproxen, diphenhydramine, methotrexate, and hydrochlorothiazide
5. History of skin cancer
6. Plan to received significant sun exposure below the 33rd parallel during study
7. Used tanning or phototherapy devices within the last 30 days
8. Vitamin D supplement use of more than 600 IU daily.

9. Systemic steroids use
10. H1 antihistamine use in the last 7 days
11. Diagnosed with light allergies (including but not limited to): actinic prurigo, polymorphous light eruption, or solar urticaria
12. Diagnosed with light sensitivities (including but not limited to): protoporphyria, photodermatitis, xeroderma pigmentosum, lupus erythematosus, chronic actinic dermatitis, or UV-sensitive syndrome

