Another study was performed on military personnel. Military personnel are at high risk for low vitamin D status which is common in individuals who regularly perform extreme physical exertion, particularly in combination with periods of psychological stress, inadequate nutrition, and sleep disruption. A total of 98 participants enrolled in the study; 10 (10.2%) either dropped out or were removed after enrollment. The final sample included 45 participants in the supplement and 43 in the phototherapy group. There were no between group differences noted based on age or gender distribution ( $P=0.06$ ). There were also no between group differences observed with respect to race / ethnicity, Fitzpatrick skin type, birth location with respect to 37th parallel, prior diagnoses of vitamin D deficiency, vitamin D supplementation history, stress fractures, or family history of bone disorders, and total number of hours per week of sun exposure, with  $P > 0.05$  for these groups.

The median serum 25(OH)D levels at baseline for the supplement and phototherapy were 25.0 ng/mL (IQR 21.0–32.0) and 28.0 ng/mL (IQR 22.0–35.0), respectively. By month three, the phototherapy group showed significantly higher levels of serum 25(OH)D than the supplement group ( $P=0.01$ ,  $\eta^2=0.08$ ) with a median level of 25.5 ng/mL (IQR 21.0–29.8) compared to a median level of 30.0 ng/mL (IQR 25.8–37.0) for the phototherapy group. By the four-month follow up the two groups again showed a slight difference in serum 25(OH)D levels with higher levels in the phototherapy group ( $P=0.04$ ,  $\eta^2=0.05$ ). At this timepoint the supplement group had decreased from baseline to median levels of 21.0 ng/mL (IQR 17.0–30.0) and phototherapy returned to baseline (median 27.0 ng/mL, IQR 22.0–32.5) (supplementary documents).

With suboptimal intake of key nutrients like calcium and vitamin D, historically low compliance with taking pills, and low sun exposure, limited potential to optimize serum 25(OH)D continues to pose a threat to physical and mental health, disease prevention, and resilience so critical to individual wellness and readiness. At a time when self-care measures are highly valued for health promotion, programmed UVB photobiologic therapy, available as a kiosk in the community, appears to be a safe, efficacious alternative to oral vitamin D supplementation.

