### 12.3 Sample Size Determination

A previous study by Chandra et al. demonstrated the increase in the mean serum 25(OH)D in subjects with malabsorption syndrome receiving UV therapy from  $21 \pm 3$  ng/mL to  $27 \pm 4$  ng/mL. According to this previous study, we postulate the mean and standard deviation of serum 25(OH)D before and after the intervention.

To achieve a power of 90% and a level of significance ( $\alpha$ ) of 0.05 (two sided), for detecting a mean of the differences of 6 between pairs, assuming the standard deviation of the differences to be 4, the sample size in this feasibility is 8.

We expect that 80% of the population in the Boston area has a level of 25(OH)D below 30 ng/ml. Thus, we have to enroll approximately 14 subjects with different group skin types to enroll 10 vitamin D deficient or insufficient subjects in this study. In our experience, the rate of screen failure and patient dropout is 10-15%. Then, we expect to have at least 8 subjects at the end of the study to achieve the desired power.

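### The vitamin D exclusions in section 7.2 have no look-back, so a volunteer who recently stopped supplements could enter with 25(OH)D still falling; this would shrink the measured gain and could take power below 90%

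*Combined protocol and SAP*

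**What the plan says.** Two of the exclusions in section 7.2 concern vitamin D. Exclusion 1 is "Ongoing treatment with supplemental or pharmacological doses of vitamin D, vitamin D metabolites or analogues". Exclusion 8 is "Vitamin D supplement use of more than 600 IU daily". The first is limited to current treatment, and the second sets a dose threshold without a period.

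Two other exclusions in the same list do look back: exclusion 7, "Used tanning or phototherapy devices within the last 30 days", and exclusion 10, "H1 antihistamine use in the last 7 days".

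The entry limit in section 7.1 is "Serum total 25(OH)D < 30 ng/mL". No wash-out or stable-intake requirement appears elsewhere in the protocol.

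All subjects receive UVB (section 9). Section 12.1 compares 25(OH)D before and after the study with a paired t-test or Wilcoxon test, and the general linear model names skin type and sex as covariates. Section 4.1.1 places the baseline sample before the first titration, in week 2. The study ends at Wk 10 (Table 2). Section 12.3 sizes the trial "for detecting a mean of the differences of 6 between pairs", with an SD of the differences of 4, two-sided alpha of 0.05, 90% power and 8 subjects.

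**The concern.** Supplement intake acts directly on the endpoint, yet it has no look-back, while two other exposures do. A person who stopped vitamin D shortly before the screening call meets neither exclusion 1 nor exclusion 8. If 25(OH)D is still falling from the supplemented level, part of that fall lies between the Wk 2 and Wk 10 samples. There is no control arm to cancel it and no covariate for supplement history.

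The 30 ng/mL limit does not close this route. In the sponsor's earlier randomised trial (section 3.1), the supplement arm had an upper quartile of 29.8 ng/mL at month three, so about three quarters of that arm would have met the limit. Section 8 describes that arm's dose as 600 IU daily for 10 weeks.

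At stake are an understated mean gain, a somewhat larger SD of the change, and lower power. Section 3.2 says this study prepares for a larger one, so an understated gain could carry forward into its planning.

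**Working it through.** **1. The plan's own figure.** Inputs from section 12.3: mean difference 6, SD 4, two-sided alpha 0.05. Power of the paired t-test comes from the noncentral t with n − 1 degrees of freedom and noncentrality (6/4)√n. It is 90.8% at n = 7, 95.1% at n = 8 and 98.7% at n = 10. The stated 8 is therefore adequate and has some slack. Allowing for 15% loss, 8/0.85 = 9.4, which rounds up to the 10 planned.

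**2. Candidate sizes for the drift.** The only related figures in the documents are the medians of the earlier trial (section 3.1):

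| Arm | Baseline | Month 3 | Month 4 | Change, month 3 to 4 |
|---|---|---|---|---|
| Supplement | 25.0 | 25.5 | 21.0 | −4.5 |
| Phototherapy | 28.0 | 30.0 | 27.0 | −3.0 |

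The fall in the supplement arm exceeds that in the phototherapy arm by 4.5 − 3.0 = 1.5 ng/mL. I use drifts D of 1.5, 3 and 4.5. None is an estimate of the rate of decline after stopping. They are differences of medians, season may contribute, and the phototherapy arm's fall may include loss of device effect.

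**3. Effect on the mean and SD.** Let a share p of subjects be recent stoppers whose change is lowered by D.

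- Expected mean change = 6 − pD
- SD of change = √(16 + p(1 − p)D²)

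For p = 0.3 and D = 4.5, the mean is 6 − 1.35 = 4.65 and the SD is √(16 + 0.21 × 20.25) = 4.50. For p = 0.3 and D = 1.5, the mean is 5.55 and the SD is √(16 + 0.21 × 2.25) = 4.06.

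**4. Power at 8 completers**, by simulation of the paired t-test (p and D are assumptions):

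| Drift D (ng/mL) | 0% stoppers | 10% | 20% | 30% |
|---|---|---|---|---|
| 1.5 | 95% | 94% | 92% | 91% |
| 3 | 95% | 92% | 88% | 83% |
| 4.5 | 95% | 88% | 80% | 70% |

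**5. The same in whole subjects.** At n = 8 and D = 4.5, one stopper gives a mean of 6 − 4.5/8 = 5.44 and power of 88%. Two give 6 − 9/8 = 4.88 and 77%. If all 10 enrolled subjects complete, power at D = 4.5 is 96% with one stopper and 92% with two.

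**6. Sensitivity to the planned gain.** The sponsor's earlier four-week device study (section 3.1) gained 27.2 − 22.8 = 4.4 ng/mL, after exposures of 0.75 MED. If 4.4 is the true gain here, with SD 4 kept as an assumption, power at n = 8 is 76% before any stopper is considered. One stopper drifting by 2 takes it to 70%, and one drifting by 4.5 takes it to 59%. The drop from 95% to 76% comes from the smaller gain and is a separate matter.

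**The case against.** A reader might infer that recent stoppers would hide the device effect, or that the planned 90% power is lost. The documents do not support either statement. In the worst cell above the expected gain is still 4.65 of 6 ng/mL. For a drift of 1.5, power stays above 90% at all three shares.

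A reader might also take the 4.5 ng/mL fall as loss of supplement-derived 25(OH)D. The phototherapy arm fell by 3.0 over the same interval. The supplement arm had risen only 0.5 above its baseline and then fell 4.0 below it, so something other than supplement loss may be involved. A seasonal fall would affect every subject, and a supplement look-back would not remove it. That trial also enrolled military personnel on 600 IU daily, a dose that exclusion 8 does not bar, so it says nothing about people stopping higher doses.

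The route in is narrow. Section 9 asks the eligibility questions by telephone and schedules only those found eligible. A person who reports current use fails exclusion 1 on that call, so a stopper must have stopped beforehand or be screened again. Intake is partly recorded: Table 2 has 25(OH)D at Wk 1 and Wk 2, a sun and food checklist and concomitant medications, and section 9 has questions on vitamin D consumption at titration visits. In ten people these could help to identify a recent stopper.

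Finally, this is a feasibility study. This particular drift works against the study hypothesis, so by itself it cannot create a false claim of benefit.

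All of this stands and lowers the importance of the point. It does not close the gap, because nothing in the plan excludes or adjusts for a recent stopper.

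**Conclusion.** The gap holds as a minor point, worth considering. Exclusions 1 and 8 leave recent stoppers eligible, and a single-arm paired comparison would count their decline against the device. The measured gain would be attenuated by pD: 0.15 ng/mL at p = 10% and D = 1.5, up to 1.35 ng/mL at p = 30% and D = 4.5. Over that range power at 8 completers runs from 94% down to 70%. It falls below the stated 90% at shares of 20% or more with a drift of 3, and at all three shares with a drift of 4.5.

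These figures rest on a true gain of 6, an SD of 4, and shares and drifts that the documents do not supply. The trial's net bias is undetermined. Regression to the mean after selection below 30 ng/mL, or season, may push the before-after change upward.

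**What to change.** In section 7.2, add to the vitamin D supplement exclusion a look-back counted from the Wk 1 screening sample. It should be no shorter than the 30 days in exclusion 7, and preferably about 8 weeks, the length of the Wk 2 to Wk 10 comparison. The documents contain no wash-out data that would fix the length, so the sponsor should set and justify it. Ask for the date of the last vitamin D dose at the telephone screen and record it at Wk 1. Exclusion 1 (any ongoing supplement) and exclusion 8 (only above 600 IU daily) do not agree with each other and must be reconciled in the same edit, so that it is clear which use the look-back covers.

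The cost is one line in section 7.2, one question on the call and one field at Wk 1. The downside is some additional screen failures or delayed starts. The documents do not allow their number to be estimated.
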